**Version history**

SAP Version	Approval Date	Protocol Version (Date) on which SAP is Based	Change	Rationale
SAP	29 Jan 2024	16 March 2023		Original version

## 1. INTRODUCTION

The purpose of this Statistical Analysis Plan (SAP) is to describe the planned analyses for TH HSV REC-004 (218459). A separate charter for the activities of the internal Safety Review Committee (iSRC) will be used.

### 1.1. Objectives, Estimands and Endpoints

Objectives	Endpoints and Estimands
Primary	
To evaluate the reactogenicity and safety of the HSVTI.	
 
Percentage of participants reporting each solicited administration site event (redness, pain, and swelling) within 7 days (Day 1-Day 7) post-each dose.
 
Percentage of participants reporting each solicited systemic event (fever, fatigue, headache, myalgia, arthralgia) within 7 days (Day 1-Day 7) post-each dose.
 
Percentage of participants reporting unsolicited AEs within 28 days (Day 1-Day 28) post-each dose.
 
Percentage of participants reporting MAEs from Dose 1 (Day 1) up to 28 days post-Dose 2 (Day 57).
 
Percentage of participants reporting SAEs from Dose 1 (Day 1) up to 28 days post-Dose 2 (Day 57).
 
Percentage of participants reporting newly diagnosed pIMDs from Dose 1 (Day 1) up to 28 days post-Dose 2 (Day 57).
 
Percentage of participants reporting exacerbation of pre-existing pIMDs from Dose 1 (Day 1) up to 28 days post-Dose 2 (Day 57).
 
Percentage of participants reporting any hematological and biochemical laboratory abnormalities at pre-study intervention administration (Day 1), post-Dose 1 (Day 8 and Day 29), and post-Dose 2 (Day 36 and Day 57).
 

Secondary	
To evaluate the humoral immune response induced by the HSVTI.	
 
CC1 antibody GMC and seropositivity rate (assessed by ELISA) at pre-study intervention administration (Day 1), 28 days post-Dose 1 (Day 29), and 28 days post-Dose 2 (Day 57).
 

To evaluate the cellular immune response induced by the HSVTI.	
 
Geometric mean of CC1 CD4+/CD8+ T-cells frequency expressing at least 2 activation markers (IFN-<math>\gamma</math>, TNF-<math>\alpha</math>, IL-2, IL-13, IL-17, 4-1BB and/or CD40L) and including at least one cytokine (assessed by CFC) at pre-study intervention administration (Day 1), 28 days post-Dose 1 (Day 29) and 28 days post-Dose 2 (Day 57).
 

To evaluate the safety of the HSVTI up to the end of follow-up period.	
 
Percentage of participants reporting MAEs from Dose 1 (Day 1) up to study end (Day 209).
 
Percentage of participants reporting SAEs from Dose 1 (Day 1) up to study end (Day 209).
 

Objectives	Endpoints and Estimands
	
 
Percentage of participants reporting newly diagnosed plIMDs from Dose 1 (Day 1) up to study end (Day 209).
 
Percentage of participants reporting exacerbation of a pre-existing plIMDs from Dose 1 (Day 1) up to study end (Day 209).
 

[figure not shown]
**AE:** adverse event; **CD4+/CD8+**: cluster of differentiation 4/8; **CD40L**: cluster of differentiation 40 ligand; **CFC**: cell flow cytometry; **ELISA**: enzyme-linked immunosorbent assay; **CCI**: geometric mean concentration; **GMC**: geometric mean concentration; **HSVTI**: HSV-targeted immunotherapy; **IFN- $\gamma$** : interferon-gamma; **IL (IL-2, IL 13, IL 17)**: interleukin; **MAE**: medically attended event; **pIMD**: potential immune-mediated disease; **SAE**: serious adverse event; **TNF- $\alpha$** : tumour necrosis factor-alpha.

## 1.2. Study Design

This is a Phase 1, randomized, placebo-controlled, observer-blind, single-country study with 3 parallel groups (refer to Figure 1):

- HSVTI\_F1 group: approximately 20 HSV-2 seronegative participants aged 18 to 40 years will receive 2 doses of HSVTI [REDACTED].
- HSVTI\_F2 group: approximately 20 HSV-2 seronegative participants aged 18 to 40 years will receive 2 doses of HSVTI [REDACTED].
- Placebo group: approximately 10 HSV-2 seronegative participants aged 18 to 40 years will receive 2 doses of placebo as control.

## Figure 1 Study Design Overview

**D:** day; **HSVTI:** HSV-targeted immunotherapy **iSRC:** internal safety review committee; **N:** number of participants; **PC:** phone call; **V:** visit; **PBMC:** peripheral blood mononuclear cell

# The iSRC evaluation will take place approximately once a month until all participants complete the Day 57 visit to review all accumulated safety data. *Ad hoc* iSRC evaluations can be triggered in case any safety concern is observed.

\* A first analysis will be performed on all data available and as clean as possible, when data for at least primary and secondary endpoints up to Day 57 are available

## 2. STATISTICAL HYPOTHESES

No formal statistical hypotheses are to be tested. All analyses will be descriptive.

### 2.1. Multiplicity Adjustment

No formal statistical hypotheses are to be tested. In general, test statistics will not be adjusted for multiple comparisons.

## 3. ANALYSIS SETS

[figure not shown]
Analysis set	Description
Screened set	All participants who were screened for eligibility
Enrolled set	All participants who entered the study (who were randomized or received study intervention or underwent a post-screening procedure)
Exposed set (ES)	All participants who received at least 1 dose of the study intervention.
Per Protocol set for analysis of humoral immunogenicity (PPS_Immuno)	All eligible participants who received all doses as per protocol, have immunogenicity results post-dose, complied with dosing/blood draw intervals, without intercurrent conditions that may interfere with immunogenicity and without prohibited concomitant medication/vaccination. The analysis will be done according to the study intervention that participants received at dose 1.
Per Protocol set for analysis of cellular immunogenicity (PPS_CMI)	All eligible participants who received all doses as per protocol, have CMI results post-dose, complied with dosing/blood draw intervals, without intercurrent conditions that may interfere with immunogenicity and without prohibited concomitant medication/vaccination. The analysis will be done according to the study intervention that participants received at dose 1.

CCI

**CONFIDENTIAL**

218459

CCI

**CONFIDENTIAL**

218459

[figure not shown]
CCI

**CONFIDENTIAL**

218459

CCI

## 4. STATISTICAL ANALYSES

### 4.1. General Considerations

#### 4.1.1. General Methodology

Enrolled participants who prematurely withdraw from study will not be replaced.

Re-screened subjects fulfilling the enrollment criteria will enter the study and be analyzed based on their latest screening results.

Confidence intervals (CIs) will use 95% confidence levels, unless otherwise specified.

In general, CIs for proportions will be calculated using the Clopper-Pearson interval method [Clopper, 1934]. All continuous data will be summarized using descriptive statistics (n, mean, standard deviation (SD), median, minimum and maximum) and categorical data will be summarized using the number and percentage of participants in each category.

#### 4.1.2. Sequence of analyses

[figure not shown]
- A **primary analysis** will be performed on all data available and when data for at least primary and secondary endpoints up to Day 57 are available.

At this point, the statistician will be unblinded (i.e., will have access to the individual participant treatment assignment). Investigators, participants and other remaining study personnel will stay blinded up to study end (i.e., day 209 and will not have access to the individual participant treatment assignment). It is possible however, due to the limited sample size, that unblinding occurs for a few participants having a specific AE or SAE (e.g., an AE/SAE occurring only in a single participant). Therefore, anyone having access to this analysis could become unblinded regarding those specific cases. This would be acceptable given the early/descriptive nature of the study and the limited number of expected unblinding. Investigators and participants will remain blinded up to study end (Day 209). The investigators will not be provided with the individual data listings or with the randomization listings until the end of study analysis.
- The **end of study analysis** will be performed when all data for primary and secondary endpoints up to study conclusion are available (Day 209). Individual listings will only be provided at this stage.
- If data for tertiary endpoints become available at a later stage, (an) additional analysis/analyses will be performed.

**CONFIDENTIAL**

218459

[figure not shown]
CCI

**CONFIDENTIAL**

218459

[figure not shown]
CCI

**CONFIDENTIAL**

218459

[figure not shown]
CCI

**CONFIDENTIAL**

218459

[figure not shown]
CCI

**CONFIDENTIAL**

218459

[figure not shown]
CCI

**CONFIDENTIAL**

218459

[figure not shown]
CCI

**CONFIDENTIAL**

218459

CCI

CCI

## **4.6. Safety Analyses**

The main safety analyses are described in Section 4.2

### **4.6.1. Additional Safety Assessments**

#### **4.6.1.1. Vital signs**

Vital signs (systolic/diastolic blood pressure, and heart rate) and pre-intervention temperature reported before each study intervention administration (Visit 1 [Day 1] and Visit 3 [Day 29]) will be summarized by group using descriptive statistics.

#### **4.6.1.2. COVID-19 Assessment**

- COVID-19 cases will be tabulated as unsolicited events

## **4.7. Other Analyses**

Not applicable.

[figure not shown]
## **4.8. Changes to Protocol- Defined Analyses**

N/A

**CONFIDENTIAL**

218459

CCI

## 6. SUPPORTING DOCUMENTATION

### 6.1. Appendix 1 Study Population Analyses

#### 6.1.1. Participant Disposition

The number of participants who are enrolled, received study intervention and in each study group will be tabulated.

In addition, the number of participants in each analysis set will be described, e.g., including the number of participants excluded from the PPS and the number who withdraw and reason for dropout.

#### 6.1.2. Demographic and Baseline Characteristics

The median, mean, range and SD of age (in years) at time of screening, height (cm), weight (kg), and BMI ( $\text{kg}/\text{m}^2$ ) will be computed by group, distribution of participants in each ~~CCR~~ category (positive/negative), race, ethnicity, and sex composition will be summarised overall and by study intervention group. This analysis will be based on the ES, the PPS\_Immuno and the PPS\_CMI at Day 1.

#### 6.1.3. Participant exposure

The number and percentage of participants who received each study intervention formulation or the placebo will be tabulated by group and by dose for the ES.

#### 6.1.4. Concomitant Medications

Medications will be coded using the GSKDRUG dictionaries.

The number and percentage of participants using concomitant medication (any medication and any antipyretic) during the 7-day and the 28-day follow-up period after each dose and overall will be tabulated with exact 95% CI.

## 6.2. Appendix 2 Data Derivations Rule

This section contains standard rules for data display and derivation for clinical and epidemiological studies.

### 6.2.1. Attributing events to study intervention doses

The dose relative to an event is the most recent study dose given to a participant prior to the start of a given event. For example, if the start date of an AE is between Dose 1 and Dose 2, the relative dose will be Dose 1.

[figure not shown]
If an event starts on the same day as a study dose, the relative dose will be derived from the additional information provided in the eCRF using the contents of the flag indicating if the event occurred before or after study dose. If 'after study dose' is selected, the relative dose for the event will be the one administered on the start day of the event. If 'before study dose' is selected, the relative dose for the event will be the dose prior to this one.

CCI

**CONFIDENTIAL**

218459

CCI

### 6.2.3. Data derivation

#### 6.2.3.1. Age at time of screening in years

Age will be calculated as the number of years between the date of birth and the date at time of screening

CCI

#### 6.2.3.2. Temperature

Temperatures will be presented in degrees Celsius (°C). Temperatures reported in degrees Fahrenheit (°F) will be converted as follows:

$$\text{Temperature (Celsius)} = ((\text{Temperature (Fahrenheit)} - 32) \times 5)/9$$

#### 6.2.3.3. Numerical serology results

Numerical serology results will be derived from the content of IS.ISORRES in the SDTM dataset. For assays with a specific cut-off, the following derivation rules apply:

IS.ISORRES	Derived value
“NEG”, “-”, or “(-)”	cut-off/2
“POS”, “+”, or “(+)”	cut-off
“< value” and value is <= assay cut-off	cut-off/2
“< value” and value is > assay cut-off	value
“> value” and value is < assay cut-off	cut-off/2
“> value” and value is >= assay cut-off	value
“value” and value is < cut-off	cut-off/2
“value” and value is >= cut-off	Value
“value” and value is > ULOQ	ULOQ
All other cases	missing

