
9.3.4. Secondary Endpoints/Estimands Analyses

The analysis of the secondary humoral immunogenicity objectives will be performed on the PPS for analysis of immunogenicity (PPS_immuno). The analysis of the secondary CMI objectives will be performed on the PPS for analysis of CMI (PPS_CMI). If more than 10% of participants are eliminated from any of the PPS in any treatment group, a sensitivity analysis will be carried out using the ES. The analysis of the secondary safety objective will be performed on the ES.

Statistical Analysis Methods
The percentage of participants with any AEs (solicited and unsolicited) resulting in a medically attended visit from Dose 1 up to study end (Day 209) will also be tabulated by MedDRA SOC and PT by group, after each dose and overall with exact 95% CI.
The percentage of participants with at least one report of SAE, with at least one report of causally related SAE, with at least one report of fatal SAE, and with at least one report of causally related fatal SAE classified by the MedDRA SOC and PTs reported from Dose 1 up to study end (Day 209) will be tabulated by group with exact 95% CI.
The percentage of participants with at least one newly diagnosed pIMD and at least one exacerbation of a pre-existing pIMD classified by the MedDRA SOC and PTs and reported from Dose 1 up to study end (Day 209) will be tabulated by group with exact 95% CI.
For each group, at each timepoint that blood samples are collected for immune responses and for each assay (unless otherwise specified):

• Seropositivity rates and their 95% CI will be tabulated.• GMCs/GMTs and their 95% CI will be tabulated and represented graphically. CCI [REDACTED]• Mean geometric fold increases and their 95% CI will be tabulated and represented graphically. CCI [REDACTED]• Percentage of participants that had a study intervention response defined as a 4-fold increase in concentration and their CI will be tabulated by group. CCI [REDACTED].• Antibody titer/concentration will be displayed using reverse cumulative curves.• The kinetics of titers will be plotted as a function of time for participants.• The frequency of specific CD4+/CD8+ T-cells will be summarised (mean, SD, minimum, Q1, median, Q3, and maximum) by group, at each timepoint during which blood samples are collected for CMI (descriptive statistics).

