10.2. Appendix 2: Clinical laboratory tests

10.2.1. Laboratory Assays Description

Descriptions of available assays are provided below. Descriptions could be subject to change, due to assay(s) being under development.

HSV serology by Western blot

CCI [REDACTED] proteins from detergent lysates of HSV infected cells are separated by electrophoresis then transferred to nitrocellulose paper. The strips of paper or 'blots' containing either separated, fixed proteins from CCI [REDACTED] are then incubated with the participant's serum. Antibodies, which bind to the viral proteins, are then detected by an enzyme-mediated color change. The pattern of staining on the 2 blots (CCI [REDACTED] [REDACTED]) is dictated by the number and identity of the HSV proteins to which the participant's immune system has responded. Thus, a predominance of staining on either the CCI [REDACTED] antigen-containing blot allows serotyping of the sera. In 80% of cases, this is all that is required. If the serotype is uncertain, the serum is adsorbed against both CCI [REDACTED] proteins, and re-run on fresh blots to obtain clearer profiles (essentially removing type common antibody) [Ashley, 1988].

CCI [REDACTED] testing by ELISA

The CCI [REDACTED] IgG ELISA is under development and the procedure could change. The assay will be based on an indirect solid phase ELISA allowing the detection and quantification of total IgG antibodies directed against the CCI [REDACTED] heterodimer in human serum samples.

The principle of this assay will be as follows: the mutated heterodimer CCI [REDACTED] antigen will be adsorbed onto a 96-well polystyrene microplate. After a washing and a blocking step, dilutions of serum samples, controls and standard(s) will be added to the coated microplate. After incubation, the microplate will be washed to remove unbound primary antibodies. Bound IgG will be detected by the addition of a secondary anti-IgG human antibody conjugated to HRP. Bound antibodies will be quantified by the addition of the HRP substrate solution, whereby a colored product develops proportionally to the amount of CCI [REDACTED] IgG antibodies present in the serum sample. The corresponding antibody concentration, corrected for the dilution factor, will be expressed in EU/mL, units arbitrarily chosen as no existing reference standard is available.

Intracellular cytokine staining

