#### 6.2.3.4. Geometric mean titers (GMTs) and concentrations (GMCs)

Geometric Mean Titer (GMT) or Concentration (GMC) calculations are performed by taking the inverse logarithm of the mean of the log titer or concentration transformations. Non quantifiable antibody titers or concentrations will be converted as described in section 6.2.3.3 for the purpose of GMT/GMC calculation. Cut-off values are defined by the laboratory before the analysis.

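### SAP 6.2.3.3 gives some censored serology results numbers that the results do not support: '< value' above the cut-off takes its upper bound, and '> value' below the cut-off takes half the cut-off

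*SAP*

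**What the plan says.** SAP 6.2.3.3 gives a conversion table for assays with a cut-off. Its scope is general: "Numerical serology results will be derived from the content of IS.ISORRES in the SDTM dataset". Writing c for the cut-off, the relevant rows are:

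- '< value' "and value is <= assay cut-off" becomes c/2.
- '< value' "and value is > assay cut-off" becomes value.
- '> value' "and value is < assay cut-off" becomes c/2.
- A plain number "and value is < cut-off" becomes c/2. A plain number at or above c keeps its value, and one above ULOQ becomes ULOQ.
- A result reported only as positive becomes c; one reported only as negative becomes c/2.

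SAP 6.2.3.4 sends the converted values into the GMT/GMC and adds: "Cut-off values are defined by the laboratory before the analysis". Protocol 10.2.1 states that the "IgG ELISA is under development and the procedure could change" and that concentrations are corrected for dilution. The readable text gives neither a cut-off nor a lower limit of quantification (LLOQ).

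Protocol Table 3 and SAP 1.1 list GMC and seropositivity rate as the humoral secondary endpoints. Protocol 9.3.4 also tabulates fold increases and the percentage of participants with a "study intervention response defined as a 4-fold increase in concentration".

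**The concern.** A '< value' result is left-censored. When the limit is above the cut-off, the true concentration may lie on either side of the cut-off, so the result does not show whether the participant is positive. The table gives it the limit itself, a number in the positive range. The mirror row makes the opposite error: a '> value' result with value between c/2 and c is known to exceed value but is coded lower than that.

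At stake are the humoral read-outs at Days 1, 29 and 57. With 20, 20 and 10 participants per group (Protocol 6.3.3), one result is enough to show in a table. Because the ELISA is still being developed and the cut-off is set later, the documents give no ground for assuming that these rows will stay empty.

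**Working it through.** The plan states no figure for this rule, so there is nothing to reproduce. The check applies the table with c = 1 as the unit.

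**Inputs.** Conversion rows: SAP 6.2.3.3. Use in the GMC: SAP 6.2.3.4. Group sizes 20/20/10: Protocol 6.3.3. Clopper-Pearson 95% intervals: SAP 4.1.1. Assumptions: one affected result, full group sizes, and limits of k times the cut-off with k from 1.01 to 8.

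**GMC.** Replacing c/2 by kc in one of n results multiplies the geometric mean by (kc ÷ c/2)^(1/n) = (2k)^(1/n).

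| k | n = 10 | n = 20 |
|---|---|---|
| 2 | 4^(1/10) = 1.149 | 4^(1/20) = 1.072 |
| 4 | 8^(1/10) = 1.231 | 8^(1/20) = 1.110 |
| 8 | 16^(1/10) = 1.320 | 16^(1/20) = 1.149 |

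**Seropositivity.** Every '< kc' result with k > 1 is coded kc > c. The table codes positives at or above c and negatives at c/2, so kc reads as positive if the rate is computed from derived values. One such result moves placebo from 0/10 (95% CI 0 to 30.8%) to 1/10 (10.0%, 0.3 to 44.5%). In an active group it would move 0/20 (0 to 16.8%) to 1/20 (5.0%, 0.1 to 24.9%).

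**Fold rise, later result censored.** Against a seronegative baseline coded c/2, the coded rise is kc ÷ c/2 = 2k:

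- k = 1.01 gives 2.02, k = 1.5 gives 3.0, k = 1.99 gives 3.98: none reaches 4.
- k = 2 gives 4.0, k = 4 gives 8.0, k = 8 gives 16.0: all count as 4-fold.

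At k = 2 the concentration is strictly below 2c, so against the coded baseline the rise is strictly below 4; the table nevertheless records exactly 4.

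**Fold rise, baseline censored.** A Day 1 result of '< 2c' is coded 2c. A post-dose value of 4c then gives 4c ÷ 2c = 2-fold. With the baseline at c/2 it would be 4c ÷ 0.5c = 8-fold. A responder can be missed.

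**Mirror row.** Suppose '> 0.8c' is reported. The table codes 0.5c, which is too low by a factor of at least 0.8 ÷ 0.5 = 1.6. Relative to the reported bound, one such result multiplies the GMC by (0.5 ÷ 0.8)^(1/n): 0.954 for n = 10 and 0.977 for n = 20. The true value is higher still.

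**The case against.** The strongest reply is that the trigger is hypothetical. SAP 6.2 introduces the appendix as standard rules, so the table has to cover every string a laboratory might report. Nothing readable says that this ELISA will report a '<' limit above its cut-off. That stands: the frequency is unknown and may be zero.

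Second, SAP 6.2.3.4 names only GMT/GMC as a use of the conversion. The text around the 4-fold response in Protocol 9.3.4 is partly redacted, as are the SAP's analysis sections and its missing-data rules for immunological and laboratory results. A separate seropositivity rule, a stricter responder rule for seronegative participants, or an exception could be there. That also stands. The effect on the rates is inferred from the general scope of 6.2.3.3; the effect on GMC is not.

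Third, a reader might infer that the table biases every humoral read-out upward. The documents do not support this: a censored baseline lowers the fold rise, and the mirror row lowers the GMC.

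Fourth, a reader might infer that an LLOQ above the cut-off would generate false 4-fold responders wholesale. It would not. If the same limit applies at both visits, baseline and post-dose negatives receive the same number and the fold rise is 1.0. A false responder needs a baseline coded c/2 and a later limit of at least 2c in the same participant.

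Finally, the study is descriptive, with no hypothesis tested, and the 4-fold response is a supplementary tabulation rather than a listed endpoint. That limits the severity but does not make the rule right.

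**Conclusion.** The point holds in a limited form. Two rows of SAP 6.2.3.3 assign numbers that the reported results do not support. This is an incorrect rule, not merely missing detail.

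If a '< value' result above the cut-off occurs, the GMC at that visit is overstated relative to c/2 by a factor of 1.15 to 1.32 (n = 10) or 1.07 to 1.15 (n = 20) per sample, for limits of 2 to 8 times the cut-off. If derived values also feed the rates, a false seropositive can arise at any limit above the cut-off. A false 4-fold responder needs a limit of at least 2c after a baseline coded c/2. It would need more under a stricter redacted rule, for example at least 4c if that rule requires four times the cut-off. A censored baseline can hide a responder.

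The documents do not show that such results will occur, or that the net bias is upward. No error rate or power is affected. The table should be corrected, but this does not threaten the study's main purpose.

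**What to change.** Revise the table in SAP 6.2.3.3 before the Day 57 analysis unblinds the statistician:

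1. **'< value' above the cut-off.** Treat as indeterminate for seropositivity. For 4-fold response, treat as indeterminate only when the limit leaves the answer open. A post-dose limit no higher than 4 times the baseline number is a non-response. A post-dose number at least 4 times a censored baseline's limit is a response. If the redacted responder rule differs, apply the same reasoning to its threshold. Run a GMC sensitivity analysis at both c/2 and the reported limit, state which value the main table uses, and report how many results are affected.
2. **'> value' below the cut-off.** Treat as indeterminate for seropositivity and never assign a number below the reported bound. The GMC sensitivity analysis should use that bound as a floor and extend above it, since the true value exceeds it.
3. **Clarification.** State that the row for results above ULOQ overrides the row for results at or above the cut-off. A numeric result above ULOQ currently meets both. Capping is clearly the intention, so this is tidying only.

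The cost is SAP wording and a few lines of programming. The downside is that a few indeterminate results drop out of the rates. If no such results occur, nothing reported changes.
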